Protocol

Study Title: Objective response detection to natural speech stimuli for optimisation of hearing aid fitting evaluation

Researcher(s): [name] [name], [name], [name] [name], [name], [name], [name], [name]

Supervisors: [name], [name], [name], [name], [name] and [name] [name]

Funder: Engineering and Physical Sciences Research Council (EPSRC)

Sponsor (if known): University of Southampton

Background

For people with hearing deficiencies, a specific and well-perceived choice of treatment is of necessity to maintain an optimal quality of life. This step is usually performed by accurately setting up a hearing aid apparatus based on subjective measurements of the hearing impaired's response (e.g. the participant has to provide a physical response when hearing a sound). This assessment cannot be performed with hearing impaired people unwilling or incapable of giving a voluntary response, such as infants or elderly people. For this reason, a myriad of objective assessment tools measuring brain responses to speech stimuli have been proposed (Easwar *et al.*, 2015; Hosseini *et al.*, 2015; Jafarpisheh *et al.*, 2015). A comparative study on how robust these tools would be for hearing aid optimisation has however not yet been performed. Besides this, some tools have only been tested on speech-like stimuli (Easwar *et al.*, 2015; Jafarpisheh *et al.*, 2015), and it would be of interest to assess their applicability to more complex speech stimuli such as sentences or running speech (e.g. from an audiobook). This study proposes to compare the robustness of objective measurements tools for brain responses to speech on a single cohort of hearing impaired volunteers under aided and unaided conditions. The study will be performed by measuring brain responses with a multichannel electroencephalogram (EEG) system whilst the participant is listening to simple or complex speech stimuli. Responses will be measured to clean speech stimuli as well as distorted speech stimuli, e.g. speech in noise. Results of this study could shed further light on how the brain processes speech and give a clear view on the quality of these objective brain response measurements. This could improve the current standards for optimally setting up hearing aid devices.

Research questions:

1. Are speech-evoked objective brain responses sensitive to hearing aid amplification?
2. Are speech-evoked brain responses sensitive to distortions in speech and can hearing aid amplification resolve issues with brain responses to distorted speech?
3. Which (statistical) tests are optimal for detection of objective brain responses to speech?
4. Are realistic speech stimuli (words or running speech) able to robustly detect brain responses compared to current clinical standards (clicks and tones)?

Method

In this exploratory study focussing on the feasibility of obtaining objective measurements of responses to speech under aided and unaided conditions, the research questions will be addressed through a series of experiments in a group of up to 40 participants (in total) with mild to moderate hearing loss in the better hearing ear. Participants will undergo a maximum of two test procedures in which they are exposed to speech or speech-like stimuli (clicks, tones, short phonemes, words, repeated sentences and/or continuous running speech such as extracts from audiobooks). Testing will be performed in a sound treated room.

Materials

Recording of the brain responses will be performed using a 32-channel EEG system (ActiveTwo, BioSemi BV, Amsterdam, Netherlands). System components will be applied as per the manufacturer's recommendations to ensure subject safety and optimal brain response recording. The system has obtained EU health and safety approval to be used for conducting research with human subjects. The experimenters will receive prior training from a member of academic staff experienced with the equipment and closely related protocols. The EEG system uses active electrodes, which means scraping of the scalp is unnecessary. This reduces the discomfort for the participants.

Participants

Participants will be 40 native English speaking subjects aged between 18 and 70 years with mild to moderate hearing loss in their better ear. Participants will be recruited from the hearing impaired cohort at the Royal Berkshire NHS Foundation Trust. Participants that might be suitable for the study will be identified from their medical records. The chief investigator, who is part of their direct healthcare team, will approach the potential participant to offer information about the study. If a participant shows interest in participating after reading the participant information sheet, an audiologist who is part of the participant's medical team will go through the participant information sheet to ensure the participant has no further questions and understands the experiment. Informed consent to participate in the study will be sought by the audiologist. Participation in the study will be entirely voluntary and subjects can be withdrawn at any time without any reason required. Subjects will be informed that they are contributing to research and that they will receive standard care in accordance with current National Institute for Health and Clinical Excellence (NICE) guidelines. Travel reimbursements up to £20 will be made.

Procedure

Experiments will take place at the Royal Berkshire NHS Foundation Trust. As a preparation, subjects will be asked to wash their hair. Before the procedure starts, the researcher performing the experiment will ask if the participant has read the appropriate Participant Information Sheet. Further to this, participants will be asked to complete a questionnaire about their hearing function and any history related to hearing dysfunction. The questionnaire will be sent along with the Participant Information Sheet and will help the researcher to assess if the participant can be included in the study and/or if specific precautions have to be made during the experiment. In the questionnaire, the participant will be asked for his gender, age, native language, current use of medication, presence of neurological diseases,

learning deficiencies, a family history of hearing loss and previous musical training as previous studies have shown that responses to sound stimuli are affected by these characteristics (Hall, 2007). We would also like to ask the participant if he/she hears better from a specific ear as taking measurements from the preferred ear could potentially optimise the responses to speech (Hall, 2007). We will further ask if the participant is aware of skin conditions or allergies as these could increase the chance of an allergic reaction to the electrode gel applied on the head for performing the EEG measurement. In case the participant is aware of severe conditions of the skin or allergic reactions, the participant will be withdrawn from the study. In cases of light skin diseases or allergic reactions the researcher will check the skin every 15 minutes to assess if an allergic reaction is occurring. We will ask the participant if he/she is suffering from tinnitus (ringing sound in the ear), current ear discomfort or infection, or has been exposed to noise in the last 24 hours, as these could influence the brain responses or make the test uncomfortable for the participant. When deemed necessary, the researcher will delay the test to a later date. Lastly, it will be asked if the participant had any ear surgery as this could lead to incompatibility with the inclusion criteria, and therefore the participant would have to be withdrawn from the study.

Informed consent will be taken from the participant when the researcher has assured the participant understands the experiment and the participant feels any questions related to the study have been answered satisfactorily.

In case their hearing function was not tested within the last 3 months before the first experiment, participants will undergo a standard clinical check-up. We will perform otoscopy on all participants and test the hearing aid of each of the participants using the test battery available at the Royal Berkshire NHS Foundation Trust. The rooms will be set up with appropriate temperature and lighting to ensure subject's comfort. In addition, participants will undergo a speech-in-noise test using the Bamford-Kowal-Bench (B.K.B.) sentence list to obtain a behavioural (subjective) response for detection of speech (Bench *et al.*, 1979). Results of this behavioural test will be compared to objective responses measured as explained below as part of the answer to question 4 of the research questions.

Application of EEG electrodes

An electrode cap appropriate to the subject's head size will be placed on the participant's head whilst ensuring correct electrode placement. After applying an electrolyte gel (recommended by the EEG system's manufacturer) to each electrode holder on the head cap using a clean gel dispenser, pin-type active electrodes will be inserted into these holders. The electrode ribbon cable will be draped over the participants shoulder (to avoid damage and trip-hazards from stepping onto it) and plugged into the Analog-to-Digital Converter (A-D) box. Additionally, individual flat active electrodes will be placed at the forehead and neck to obtain a reference signal. Individual flat electrodes for measuring eye movement will also be applied around the eyes, and one electrode will be placed under the chin to measure muscular activity due to swallowing. Eye and chin electrodes will be used to identify EEG signal segments which contain artefact and need to be removed for further analysis. The individual electrodes will be plugged into individual sockets available on the EEG A-D box.

After checking the impedance of all electrodes are in range of a reference (Common Mode Rejection-Driven Right Leg) electrode to ensure participant safety and data quality, measurement will start. Participants will be asked to sit in a reclining sofa for the measurements and a rolled towel can be provided for neck comfort. Data will be recorded with the software provided by the EEG system manufacturer.

Stimuli

Types of stimuli

Participants will be exposed to three types of stimuli during the test:

1. Short stimuli (tones, clicks or phonemes such as /da/ in Cunningham *et al.*, 2001). These stimuli have been generated for previous research studies at the ISVR to elicit brain responses.
2. Words or Short sentences taken from the B.K.B (Bench *et al.*, 1979), the Hearing in Noise Test (HINT, Nilsson *et al.*, 1994) sentence list or the matrix test developed at Imperial College London by the research group and based on previous research (for review, see Kollmeier *et al.*, 2015). These tests are generally used for assessment of speech perception in noise during hearing tests.
3. Segments of auditory recording from free audiobooks (found on <https://librivox.org/> or taken from previous studies at the ISVR and the Institute of Hearing Research) will be used. Audiobook segments have been used in various published research related to speech perception and speech intelligibility analysis (Ding and Simon, 2013).

Stimuli will be presented as clear stimuli or degraded by adding noise at different signal-to-noise ratios (SNRs), or by applying signal processing methods that emulate hearing impairment or speech processing in hearing aids.

Stimulus presentation

Stimuli will be presented at maximally 80 dB (A) through loudspeakers. According to the ISVR Task report on noise and vibration ethics (ISVR Technical Memorandum No. 808, 1996), sound levels must be less than 76 dB (A) for an 8 hour exposure during a 24 hour period, to be considered 'usual'. Participants will undergo sessions where the listening time will be maximally 2 hours at a maximum intensity of 80 dB (A). Stimuli can therefore be considered as usual.

Stimulus levels will be controlled using the calibration procedural approach as per ISO 389-8:2004. These settings of the calibration signal directly control the level of the test stimuli. Calibration will be performed at the beginning of the experimental period and every 4 weeks thereafter.

Test procedure

For this study, participants will be asked to participate in two tests. One of the tests will focus on detecting responses to short stimuli (clicks, phonemes and words). A second test will focus on detecting responses to more complex stimuli (tones, sentences and running speech). Tests will be randomised, and be performed with an interval of at least 24 hours between tests.

Test 1: Short stimuli

After participants are sat in the chair and the EEG electrode are fitted, participants will be asked to listen to click stimuli played from a loudspeaker placed 1 meter directly in front of them. Participants will not wear their hearing aid (unaided condition) for this part of the procedure. This part of the study will take about 10 minutes. Clicks would be considered the gold standard for robustness of response detection and used to answer question 4 of the research questions.

After collecting the click stimuli, participants will be asked to listen to repeated word stimuli under aided and unaided conditions. Word stimuli have been used in previous

experiments with normal hearing participants and showed good detection rate of brain responses. Words will be played as normal and distorted words. Distortions will include high-pass filtered (frequencies above 1000 Hz only) and low-pass filtered (frequencies below 1000 Hz only) versions of the words and words mixed with noise at different signal-to-noise ratios. Each participant will be exposed to 6 conditions listed below, each lasting 7 minutes, in aided and unaided conditions. This means that the total test time will be 12 conditions of 7 minutes, or 84 minutes. Conditions will be randomised during the study. Breaks will be offered between the tests, but researchers will make participants aware they can ask for a break at any time during the procedure. Participants will also be allowed to sleep during this part of the study.

To summarise: the different word conditions are

1. Clean words in quiet
2. Clean words in noise (SNR = 0dB)
3. Clean words in noise (SNR = 3dB)
4. Low-pass filtered words in quiet (0-1000 Hz)
5. High-pass filtered words in quiet (>1000 Hz)
6. High-pass filtered words in quiet (>2000 Hz)

These will be repeated in aided and unaided conditions. This would help in answering questions 1 and 2 of the research questions.

Test 2: Complex stimuli

For this part of the study, participants will be asked to listen to tones and running speech presented from a loudspeaker at 1 meter distance directly in front of them. Running speech will be a segment of about 20 minutes. Participants will be asked to remain attentive during this tests, as we will be measuring cortical responses to speech. To ensure this, they will be asked to answer multiple choice questions regarding the content of the speech presented at random intervals. Participants will perform the experiment twice under aided and unaided conditions. Therefore, a total of 80 minutes of EEG signal to running speech will be collected per participant. Results would be used to answer question 1 and 2 of the research questions.

Lastly, modulated tones will be presented at frequencies of 1000 Hz under aided and unaided conditions at intensities of 40, 60 and 80 dB (A). Tones will be modulated with a modulation frequency of 40 Hz for 6 minutes. Total test time over the entire test 2 procedure will therefore be 92 minutes. For each of the tones, we will ask the participant to rate its loudness on a seven-point scale ranging from very soft to very loud (Castro, *et al.* 2008). This could be used to help answering question 4 of the research questions.

End of experiment

By the end of the recording session all of the equipment, electrodes, insets and cap will be removed gently from the participant by the researcher. Equipment will be cleaned following the manufacturer's recommendations. At the end of the procedures, the experimenter will give information to the participant about the possibility to become part of a database collecting contact information for participants for future studies at the Royal Berkshire NHS Foundation Trust or University of Southampton.

Data analysis

Data analysis will be performed off-line. Pre-processing and artefact rejection will be performed according to current standards in the research field. Data from tests consisting of repeated stimulus sweeps will be averaged over all sweeps to allow analysis of brain responses. For all tests, the relationship of the response to the

speech stimulus will be performed by comparing the stimulus envelope with spectro-temporal features in the (averaged) brain response. Further analysis will include assessment of coherence and delay measurements between EEG channels during brain responses, as well as temporal and spectral assessment tools and source separation techniques.

Statistical analysis

Power calculation

This is a feasibility study, and the research team is only aware of 1 study by Easwar et al (Ear and Hearing. 2015) comparing detection success rate and detection time for words stimuli during aided and unaided listening conditions is available, with only one word stimulus used in this study. The smallest significant difference in response amplitude between aided and unaided conditions at conversational level was 35 nano-volts (nV) with a within-group standard deviation of 30 nV). Based on these findings, the current study would need to include 29 participants for an ANOVA study to have a power of 80% at an alpha level of 0.01. From analysis of cortical responses to running speech in normal hearing participant, we expect larger variability compared to the results found for words, which led us to decide on a participant number of 40.

Statistical analysis of data

Prior to analysing the results, their normality will be tested. This will guide decision on using parametric or non-parametric statistical tests. Temporal relations between responses will be quantified with correlation analysis. Robustness of responses to noise level will be assessed with an F-ratio test. Statistical significant relationships between EEG channels and the stimulus will be tested using analysis of variance measures. Statistical signal processing methods (including bootstrap methods and confidence limits) will be used in detecting responses.

References

Castro, F.Z., Barajas de Prat, J.J., Zabala, E.L. 2008. Loudness and auditory steady-state responses in normal-hearing subjects. *International Journal of Audiology*, 47:5, 269-275.

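### Research question 4 compares speech with clicks and tones recorded for different lengths, and no matched-length analysis is planned, so a difference in detection partly reflects recording time

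*Combined protocol and SAP*

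**What the plan says.** The fourth item under Research questions is comparative: "Are realistic speech stimuli (words or running speech) able to robustly detect brain responses compared to current clinical standards (clicks and tones". The recordings that serve it are described in separate places.

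- **Clicks** (Test 1: Short stimuli). "Clicks would be considered the gold standard for robustness of response detection and used to answer question 4 of the research questions". On length: "This part of the study will take about 10 minutes". On aided state: "Participants will not wear their hearing aid (unaided condition) for this part of the procedure".
- **Words** (Test 1). Six conditions, "each lasting 7 minutes, in aided and unaided conditions".
- **Running speech** (Test 2: Complex stimuli). A segment of about 20 minutes, heard twice aided and twice unaided, for a stated total of 80 minutes.
- **Tones** (Test 2). Three levels, aided and unaided, with a duration of 6 minutes. Test 2 as a whole is said to take 92 minutes.

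Data analysis says that every sweep of a repeated stimulus enters the average. It does not clearly apply this to running speech, for which no analysis length is given. Statistical analysis of data names bootstrap methods and confidence limits for detecting responses, without a recording length or aided state. Detection time appears only under Power calculation, as something an earlier study compared.

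Two other inputs serve question 4. For the speech-in-noise test, Procedure says: "Results of this behavioural test will be compared to objective responses measured as explained below as part of the answer to question 4". Loudness ratings of the tones may also contribute. Neither sets a length or aided state for the EEG comparison.

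**The concern.** Averaging lowers residual noise as recording time grows. Of two stimuli that evoke equally strong responses, the one recorded longer will therefore be detected more often. If each stimulus is analysed at its full length, a difference in detection rate mixes what the stimulus does with how long it was played.

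The direction is not constant. Length favours clicks over words, but running speech over both clicks and tones. At stake is any statement that a realistic speech stimulus is detected better, or worse, than a clinical standard. Whether a response can be detected with the procedure as run is not in doubt on this ground.

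**Working it through.** **Step 1. Reproduce the stated times.**

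- Words: 6 conditions × 2 aided states × 7 min = 84 min, as stated.
- Running speech: 2 runs × 2 aided states × 20 min = 80 min, as stated. Each aided state therefore has 40 min.
- Tones: 92 − 80 = 12 min, or 6 min per aided state. Over three levels this is 2 min per level if split evenly. Six minutes at every level would give 80 + (3 × 2 × 6) = 116 min, not 92.

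The tone length is thus 6 or 2 min, depending on how these figures are reconciled. All lengths are nominal; accepted EEG after artefact rejection will be shorter.

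**Step 2. Signal-to-noise factor from length alone.** If residual noise falls as 1/√T, the factor is √(T1/T2).

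| Comparison | Minutes | Factor |
|---|---|---|
| Clicks v words | 10 v 7 | 1.20 |
| One running-speech run v clicks | 20 v 10 | 1.41 |
| Both runs v clicks | 40 v 10 | 2.00 |
| One run v tones | 20 v 6 | 1.83 |
| Both runs v tones | 40 v 6 | 2.58 |
| One run v tones | 20 v 2 | 3.16 |
| Both runs v tones | 40 v 2 | 4.47 |

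**Step 3. What this could do to detection rates (illustration only).** The document gives no amplitudes, noise levels or detection rates by stimulus, so a model has to be assumed: the same response strength per minute for every stimulus, a detector following a chi-square distribution with 2 degrees of freedom tested at 5%, and a noncentrality proportional to T. The noncentrality is set so that 7 minutes gives the base rate in the first column: 2.776, 4.957, 7.702, 12.654 and 15.443 in turn.

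| Base rate at 7 min | 2 min | 6 min | 10 min | 20 min | Gap, 20 v 10 (points) | Gap, 20 v 6 (points) |
|---|---|---|---|---|---|---|
| 30% | 11.5% | 26.2% | 41.2% | 71.4% | 30 | 45 |
| 50% | 17.1% | 43.8% | 66.1% | 93.1% | 27 | 49 |
| 70% | 24.5% | 62.8% | 85.3% | 99.2% | 14 | 36 |
| 90% | 38.0% | 84.7% | 97.5% | >99.9% | 3 | 15 |
| 95% | 45.3% | 91.3% | 99.2% | >99.9% | 1 | 9 |

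For clicks against words, the 10-minute rate minus the base rate gives about 16 points at a 50% base rate (66.1 − 50) and 4 points at 95% (99.2 − 95). With 1, 2, 4 or 10 degrees of freedom, the 20 v 10 gap stays between 26 and 28 points at a 50% base rate and between 2 and 3 points at 90%.

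A second detector, a one-sided normal test, gives the same picture: 50% detection at 10 min becomes 83% at 20 min at a 1% level, or 75% at a 5% level.

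**Step 4. Aided state.** Clicks are recorded unaided only. Words, running speech and tones are recorded both ways. An unaided comparison of all four is therefore available from the planned data; what is missing is a sentence saying that question 4 uses it.

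**The case against.** The study calls itself exploratory and a feasibility study, and question 4 can be read as benchmarking each test as it is normally run. On that reading full-length detection is the quantity wanted. This stands, and the full-length result should be kept.

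Equal minutes are also not equal information. Clicks, words, tones and running speech differ in number of sweeps and in response type. Attention differs too: for the words, "Participants will also be allowed to sleep during this part of the study", whereas Test 2 asks participants to stay attentive. Equal strength per minute, assumed in the illustration, is close to what the study would have to find out. This also stands: a matched-length result removes one confounder, not all of them, and should not be the sole basis for a claim.

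Detection may already be high. Test 1 says that words in earlier experiments "showed good detection rate of brain responses". If so, the gap between running speech and clicks nearly vanishes. But that experience was in normal-hearing participants and comes without a figure, and this cohort has hearing loss. Against 6-minute tones, 15 points remain at a 90% base rate.

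A reader might infer more than the document supports. It does not follow that no like-for-like aided state exists, since unaided recordings of all four stimulus types are planned. Nor does it follow that the design favours speech throughout: for words against clicks, length works against words, so the comparison is conservative for them.

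**Conclusion.** The concern holds as a gap in the analysis plan. With full-length averaging and no matched-length or time-to-detection analysis, a difference in detection between stimulus types partly reflects recording time. The signal-to-noise factors, 1.20 to 4.47, rest only on the nominal lengths and on noise falling with the square root of time.

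The size in detection rates is not known. For one running-speech run against clicks it could be near 30 points or near zero, depending on base rates the document does not give. The largest gaps, such as 76 points for 20 v 2 min at a 50% base rate (93.1 − 17.1), need the 2-minute reading of the tone duration and should not be quoted as expected.

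A reader might conclude that the full-length results are invalid. They are not: they show whether each response can be detected with the recording as planned. What they cannot do alone is attribute a difference to stimulus type.

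**What to change.** For question 4, add to the statistical section a within-participant comparison in the unaided state, reported beside the full-length results:

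- Show detection against accepted recording time and read it at the pairwise common length: 7 min for clicks v clean words, 10 min for clicks v running speech, and the tone length for tones v speech.
- Reconcile the 6-minute and 92-minute figures in Test 2 before setting the tone length. Treat a 2-minute tone comparison as descriptive.
- Fix in advance which segment is used (for example, the first accepted minutes of the first unaided run) and which tone level.
- Do not attribute a full-length difference to stimulus type unless the matched-length result is shown with it.
- State as limitations that matching minutes does not match number of sweeps, response type or attention.

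The cost is a little more off-line analysis of data already planned, and lower precision at the matched lengths. One running-speech run loses 1 − √(10/20) = 29% of its signal-to-noise ratio at 10 min, and clicks lose 1 − √(7/10) = 16% at 7 min. Against tones, words lose 1 − √(6/7) = 7% at 6 min but 1 − √(2/7) = 47% at 2 min, which is why the latter should stay descriptive.

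### Does the conclusion that the stimuli are 'usual' fail because it leaves out hearing-aid amplification?

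*Combined protocol and SAP*

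**What the plan says.** The exposure argument is in the section Stimulus presentation and has three inputs.

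- Level: "Stimuli will be presented at maximally 80 dB (A) through loudspeakers".
- Criterion, taken from an institutional technical memorandum: "sound levels must be less than 76 dB (A) for an 8 hour exposure during a 24 hour period, to be considered 'usual".
- Duration: "Participants will undergo sessions where the listening time will be maximally 2 hours at a maximum intensity of 80 dB (A").

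From these the protocol concludes: "Stimuli can therefore be considered as usual". The calibration described next governs the level of the test stimuli. It does not mention the output of a hearing aid.

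The test descriptions then set out how much listening is aided. In Test 1 the clicks (about 10 minutes) are unaided only. For the words, "Each participant will be exposed to 6 conditions listed below, each lasting 7 minutes, in aided and unaided conditions". For running speech in Test 2, in segments of about 20 minutes, "Participants will perform the experiment twice under aided and unaided conditions". Modulated tones are presented "under aided and unaided conditions at intensities of 40, 60 and 80 dB (A"), and "Total test time over the entire test 2 procedure will therefore be 92 minutes".

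The Procedure section adds otoscopy for everyone, a test of each participant's hearing aid, a clinical check-up if hearing was not tested in the previous 3 months, and questions on tinnitus, ear discomfort and recent noise, with the option of delaying the test.

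**The concern.** The conclusion rests on the loudspeaker level alone, while the study is built around comparing aided with unaided listening. An aid raises the level at the ear, and the margin at the 2-hour cap is only 2 dB. The 80 dB(A) maximum is also planned with the aid on, at least for the tones. If the criterion is meant at the ear, the protocol's only statement on noise exposure would leave out close to half of the listening time, in people who already have hearing loss.

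**Working it through.** **1. The protocol's own conclusion.** It prints no 8-hour equivalent and no time-level trading rule. With equal-energy trading (an assumption):

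80 − 10·log10(8/2) = 80 − 6.02 = 73.98 dB(A), which is below 76.

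With 4 or 5 dB per halving of time, 2 hours is two halvings of 8 hours, so the results are 80 − 8 = 72.0 and 80 − 10 = 70.0 dB(A). For the loudspeaker signal the conclusion holds under all three rules.

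**2. The aided share.**

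- Test 1: 6 × 7 = 42 aided minutes out of 10 + 84 = 94, or 44.7%.
- Test 2: 40 minutes of speech plus 6 of tones aided, out of 92, or 50%.
- Both tests: (42 + 46)/(94 + 92) = 88/186 = 47.3%.

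So 'about half' is correct.

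**3. How much gain would use up the margin, if the criterion applied at the ear?** The protocol gives no gain, so only a break-even value can be found:

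G = 10·log10[(480 × 10^7.6 − U) / A]

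Here U and A are the sums of minutes × 10^(L/10) over unaided and aided listening, and 480 × 10^7.6 = 1.911 × 10^10. Tones are at their stated levels. One gain is applied to all inputs. The levels of clicks, words and speech are not stated, so a maximum of 80 and an assumed 65 dB(A) are shown.

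Test 1 at 80 dB(A): U = 52 × 10^8 and A = 42 × 10^8, so G = 10·log10(13.91/4.20) = 5.2 dB.

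Test 1 at 65 dB(A): U = 52 × 10^6.5 = 1.64 × 10^8 and A = 42 × 10^6.5 = 1.33 × 10^8, so G = 10·log10(142.6) = 21.5 dB.

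| Session | Clicks, words, speech at 80 dB(A) | at 65 dB(A) (assumed) |
|---|---|---|
| Test 1, 94 min | 5.2 dB | 21.5 dB |
| Test 2, 92 min (2 min per tone level) | 5.5 dB | 17.6 dB |
| Test 2, if each tone level lasts 6 min | 5.0 dB | 14.0 dB |

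The trading rule matters too. At 80 dB(A) throughout Test 1, the 4-dB rule gives 52 × 2 = 104 unaided and 42 × 2 = 84 aided units against a budget of 480. Then G = 4·log2(376/84) = 8.7 dB. The same steps with the 5-dB rule give 12.1 dB.

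**4. How far these figures can be trusted.** Applying one gain to every input level is a strong simplification. With speech at 65 dB(A) in the 92-minute Test 2, the aided input energy is 40 × 10^6.5 + 2 × (10^8 + 10^6 + 10^4) = 3.285 × 10^8. The 80 dB(A) tone supplies 2.0/3.285 = 61% of it, so that break-even mostly describes the gain on a 2-minute tone. The speech-in-noise test in the Procedure section is not counted, because its level, length and aid status are not given. The documents can show that the answer depends on gain. They cannot say on which side of the criterion any participant falls.

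**The case for a change.** The best case for a change is this. The protocol chose to argue from a number and from the worst-case level, so the aided half should be tested on the same basis. At that level about 5 dB of gain would be enough to reach 76 dB(A) under equal-energy trading. The hearing-aid test in the Procedure section is tied to no output limit and does not say that output is recorded, so it does not supply the missing step. Participants are already hearing-impaired, and a recalculation with a few sentences costs little.

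Part of this stands. A reader cannot verify 'usual' for the aided minutes at the ear, and the safeguards listed are not a calculation.

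Two parts do not stand. First, the sentence describes the stimuli, defined there by their loudspeaker level, and that level is subject to the same maximum with or without the aid. To call it a failed claim about level at the aided ear presumes that the criterion is defined at the ear, and the documents do not say so. Second, the remedy is not always cheap. Beyond a sentence naming the reference point, it means a calculation from each participant's aid output, possibly with an added measurement per participant, and that would serve no purpose if the criterion is a sound-field one.

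**Conclusion.** No change to the plan follows. The stated conclusion is correct for what it describes: 74.0 dB(A) over 8 hours against 76, assuming equal-energy trading, and lower still under 4-dB or 5-dB trading. The documents contain no wrong figure, no contradiction on exposure and no demonstrated exceedance. They also do not show that aided listening meets the criterion at the ear. The break-even gain spans about 5 to 21.5 dB under equal-energy trading alone, and rests on assumed presentation levels, a uniform gain and an ear-level criterion, so the issue cannot be sized from the documents.

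What is left is a missing detail: the point at which the criterion applies. Whoever holds the cited memorandum can look this up, and the aided checks in the Procedure section go ahead either way. No estimate, test or sample-size input depends on it. The assessment would change if the memorandum defined its criterion at the aided ear and the aids' output at the levels actually used were shown to exceed it. The documents establish neither.
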